7.9 Collection, storage and analysis of clinical samples

All blood samples will be taken and delivered immediately for process in a CPA NHS laboratory at the individual study site. Processing of blood samples will follow the NHS laboratory protocols in keeping with Good Laboratory Practice. If consented for the optional sample sub-study, samples will be stored within the research secure repository within the trust in keeping with standard research protocols.

Please refer to the laboratory manual for details of sample collection, storage and destruction protocols.

Sampling methods include:

Faecal and blood samples will be collected at base line and days 2, 3, 5 and 12 postoperatively. Surgical resections will be collected at time of surgery.

1. Faecal samples will be collected in universal tubes 2-3 tubes per patient and put on ice until transferred to -80 freezer.
2. Serum will be prepared from the blood samples as follows:

Collect blood in a sterile 15 ml test tube or a plastic vacutainer containing no anticoagulants.

Incubate tubes in an upright position at room temperature for 30-45 minutes (no longer than 60 minutes). This will allow enough time for the blood to clot.

If using vacutainers with clot activators such as the BD Vacutainer Plus Plastic Serum Tube (red top), invert carefully 5 times before incubation.

Centrifuge tubes at 1500 x g for 10 minutes with the break OFF.

Use Pasteur pipette to carefully transfer equal amount of the supernatant into two cryotubes without disturbing the cloudy cell layer below the supernatant (10 ml of whole blood produces 4-6 ml of serum).

Immediately store tubes in -80 freezer.

Serum samples will be tested for chemokines and inflammatory markers by Multiplex immune assays.

3. Surgical resections will be collected in 2ml tubes on ice (preferably liquid nitrogen or dry ice) and immediately frozen in -80 freezer.

Tissue resections will be used to determine the expression of immune cells and their activation markers as well as proliferation and apoptotic markers using immunofluorescence microscopy. Resections will also be used to study the microbiome using 16s-rRNA gene sequencing and taxonomic analysis to determine changes in probiotic and pathogenic bacterial populations.

4. Paraffin embedded sections will be collected from the pathology archives at a later date.

Paraffin embedded sections may also be used to determine the expression of inflammatory markers using immunohistochemistry.

7.10 End of trial

The end of trial will be defined as the date of the last study visit of the last patient undergoing the trial. The sponsor will notify the MHRA of the end of the trial within 90 days of its completion.

8 TRIAL TREATMENTS

8.1 Name and description of the medicinal product

The study intervention treatment is oral ferric maltol (Feraccru®). The recommended dose is one 30mg capsule twice daily, morning and evening, on an empty stomach. Feraccru is indicated in adults for the treatment of iron deficiency. No dose adjustment is needed in elderly patients or patients with renal impairment (eGFR ≥ 15 ml/min/1.73 m²). The control group will receive standard care only. Any treatments will be at the discretion of the patient's usual clinical team. The study treatments will be randomly allocated in a 1:1 fashion but there will be no blinding of the treatment

8.2 Regulatory status of the drug

The marketing authorisation holder for Feraccru is Norgine B.V. Amsterdam, Netherlands (MA number EU/1/15/1075/001)

8.3 Product Characteristics

The Summary of Product Characteristics will be used to inform the clinical management of ferric maltol. Accessed via <https://www.medicines.org.uk/emc/product/2083/smpc>.

8.4 Drug storage and supply

The drug will be stored in Trials Pharmacies at each study site. At all sites the drug will be stored in a temperature-controlled room below 25°C. The study drug will be donated by Norgine Ltd.

8.5 Dosage schedules

Participants in the intervention arm will take one 30mg capsule twice daily, morning and evening, on an empty stomach. Treatment will commence as soon as postoperative anaemia is confirmed on day 2, 3 or 5 blood tests provided oral intake has been resumed and will continue until the first routine outpatient visit. If a dose is missed the subject will be allowed to take their missed dose within 6 hours of the correct time. If there is any interruption to treatment, for

example due to vomiting or illness, the patient will be asked to recommence treatment as soon as they are deemed safe to do so by a medical practitioner.

8.6 Known drug reactions and interaction with other therapies

Oral iron is known to reduce the absorption of penicillamine, bisphosphonates, ciprofloxacin, entacapone, levodopa, levofloxacin, levothyroxine (thyroxine) moxifloxacin, mycophenolate, norfloxacin and ofloxacin. If applicable, these medicinal products will be given at least 2 hours apart from Feraccru. Absorption of both iron and antibiotic may be reduced if oral iron is given with tetracycline. Administration of Feraccru and tetracyclines will be separated by 2 to 3 hours. Absorption of oral iron may also be reduced by calcium and magnesium salts (such as magnesium trisilicate). Administration of Feraccru with such compounds will be separated by at least 2 hours.

8.7 Concomitant medication

Throughout the study, investigators may prescribe any concomitant medications or treatments deemed necessary to provide adequate supportive care. Any medication, other than the study medication, taken during the trial will be recorded in the CRF. Participants who are on existing oral iron supplementation at time of recruitment to the trial will stop taking this as prescribed for the duration of the study and after discussion with the patient.

8.8 Assessment of compliance with treatment

Participants will self-administer the oral ferric maltose tablets. Patients will be asked to declare their compliance with the study drug during the final follow up study visit. If there is a high level of non-compliance (<70%), the patient will be included in the trial under the intention-to-treat-analysis. The reasons for non-compliance will be documented in the CRF.

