3.3 Outcome measures/endpoints

3.3.1 Primary endpoint/outcome

Study feasibility will be the primary endpoint. No a priori criteria will be used to determine study feasibility. We will use the data generated by PICoC to determine the sample size and outcome measures of a definitive trial

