10.3.2 Primary outcome analysis

The primary objective will be assessed using feasibility outcomes measures. This will include the number of eligible patients (pre-screening eligibility), willingness to be recruited to study (acceptability), willingness to be randomised (acceptability/concordance), study exclusion (screen failure rates), withdrawal of patients (non-concordance), compliance with the randomised treatment, study retention (retention rates), number of patients recruited over a given time (recruitment rate), and completion of outcome measures.

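### Compliance, one of the outcomes behind the primary feasibility objective, rests on a single unverified self-report with no defined scale or denominator, so sorting patients at 70% is unreliable

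*Combined protocol and SAP*

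**What the plan says.** Section 10.3.2 (Primary outcome analysis) includes "compliance with the randomised treatment" in the measures that will assess the primary objective. The four-item lists in the trial summary and Section 3.1 do not mention it.

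Section 8.8 is the only place where measurement is described. It states "Participants will self-administer the oral ferric maltose tablets" and then "Patients will be asked to declare their compliance with the study drug during the final follow up study visit". It continues: "If there is a high level of non-compliance (<70%), the patient will be included in the trial under the intention-to-treat-analysis". Reasons for non-compliance go into the CRF.

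Section 3.3.1 adds: "No a priori criteria will be used to determine study feasibility".

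On the planned course, Section 8.5 states: "Participants in the intervention arm will take one 30mg capsule twice daily, morning and evening, on an empty stomach". Treatment starts once anaemia is confirmed on day 2, 3 or 5 and oral intake is back. Section 8.5 ends it at the first routine outpatient visit, which Section 7.7 puts at 8 to 12 weeks after surgery. Section 4 and the trial summary give 12 weeks.

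The schedule of procedures (Appendix 1) has a row for dispensing. It has none for drug return, a capsule count, a diary or a compliance check. Drug charts are source documents under Section 11.1, but nothing ties them to compliance, and they could cover inpatient doses only.

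**The concern.** A patient who knows they are on study drug is asked once, after some two to three months of twice-daily self-dosing, how well they took it. The plan does not say whether the answer is a percentage, a number of missed doses or a yes/no, nor what the 70% is a percentage of. Nothing planned can check the answer.

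Asking only at the final visit also risks losing the answer from those who stop early. Section 7.8 withdraws patients who must discontinue for an adverse event or are lost to follow-up. Section 9.2 provides an end-of-study assessment for patients who come off treatment because of an adverse event, but does not say that compliance is asked there.

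The estimate is meant to inform a definitive trial. If it is too high, that trial would be planned on better drug exposure than it will achieve, and its treatment effect would be diluted.

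**Working it through.** The plan gives no compliance figure to reproduce. The check sets out what the 70% level would mean in capsules and how far it depends on points left open.

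**Inputs.** Two capsules a day (8.5). Start day s = 2, 3 or 5 (8.5). End at w = 8 to 12 weeks (7.7 with 8.5), or w = 12 (Section 4, trial summary). About 20 patients in the intervention arm (10.1). The control arm takes no study drug, so the measure applies to at most about 20 people.

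**Planned capsules** = 2 × (7w − s); the **70% level** is 0.70 times that.

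| End | Start | Planned | 70% level |
|---|---|---|---|
| 8 weeks | day 2 | 2 × 54 = 108 | 75.6 |
| 8 weeks | day 3 | 2 × 53 = 106 | 74.2 |
| 8 weeks | day 5 | 2 × 51 = 102 | 71.4 |
| 12 weeks | day 2 | 2 × 82 = 164 | 114.8 |
| 12 weeks | day 3 | 2 × 81 = 162 | 113.4 |
| 12 weeks | day 5 | 2 × 79 = 158 | 110.6 |

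The denominator varies by a factor of 164/102 = 1.61. A later start, if oral intake is delayed, would lower it further.

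**What recall has to resolve.** A patient stays at or above 70% with up to 0.30 × 102 = 30.6, so 30, missed capsules on the shortest of these courses, and up to 0.30 × 164 = 49.2, so 49, on the longest.

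**Effect of the undefined end of treatment.** Take a patient who starts on day 2, is seen at 8 weeks and has taken all 108 capsules. Against a course ending at that visit, compliance is 108/108 = 100%. Against a 12-week course it is 108/164 = 65.9%, below the line. The same behaviour falls on either side of 70% according to which section is followed.

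**Sensitivity to over-declaration (assumed values; the documents give none).** Two quantities must be kept apart.
- One patient's compliance: over-declaring by 5, 10 or 20 points makes a declared 70% a true 65%, 60% or 50%.
- The share of patients at or above 70%: if the true share is 60% and a fraction f of the rest declare themselves compliant, the observed share is 0.60 + 0.40f. That is 70% for f = 0.25 and 80% for f = 0.50.

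**The case against.** The strongest reply is that little hangs on the 70%. It is not a progression threshold: Section 3.3.1 sets no feasibility criteria in advance, and Section 8.8 keeps patients below 70% in the intention-to-treat analysis. Misclassification changes no analysis set, stopping rule or stated decision. This stands. A reader might infer from 8.8 and 10.3.2 together that the feasibility outcome is judged against 70%; the documents do not support that.

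Nor do they support saying that self-report cannot be set against 70% at all. A patient can declare a percentage or a number of missed doses. The comparison would be imprecise and unverifiable, not impossible.

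Self-report is also not the only evidence on whether patients can take the drug. Adverse events are assessed at baseline and every later visit, and reasons for withdrawal and non-compliance are recorded. That stands for tolerability, a secondary objective with its own data. It does not supply the amount taken.

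One could add that sampling error with about 20 patients swamps the problem: 14 of 20 compliant has an exact 95% interval of 45.7% to 88.1%. But an interval shows sampling error only. Reporting bias would stay hidden at any sample size without a reference measure.

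Finally, a capsule not returned is not proof of a capsule swallowed, so a count can overstate intake too. This is true, and limits what the fix can claim.

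**Conclusion.** The point holds as a measurement weakness. A compliance outcome used for the primary objective has one planned source, an unverified declaration after about 8 to 12 weeks, with neither scale nor denominator defined. On the documents' own dosing the course is about 102 to 164 capsules and the 70% level about 71 to 115, so classification at 70% is unreliable. These figures assume a start on day 2 to 5 and an end at 8 or 12 weeks.

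That compliance will be overstated is a plausible inference from the open-label design and self-report to trial staff. It is not shown, and its size is unknown; the shifts in the working rest on assumed values. The label of high non-compliance with below 70% beside it may look like an inverted threshold, but it reads naturally as compliance below 70% and is only a drafting slip.

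The consequence is limited to the validity of the compliance estimate carried into the definitive trial. The change is worth making because it is cheap and cannot be made after packs have been thrown away.

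**What to change.** In Section 8.8 and the schedule of procedures:

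- Ask intervention patients to bring all packs to the existing final visit, or to the end-of-study assessment if they stop early.
- Define compliance as (capsules dispensed − capsules returned) / capsules planned, from the actual start date to the protocol-defined end of treatment.
- Report medically directed interruptions (Section 8.5 foresees pauses for vomiting or illness) separately, so that they are not read as patient non-compliance.
- Reword the label as compliance below 70%.
- Keep the self-report and the reasons as supporting data, and as the flagged fallback when packs are not returned.

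Reconcile the end of treatment between Section 4 and the trial summary (12 weeks) and Sections 8.5 and 7.7 (first routine outpatient visit, at 8 to 12 weeks), because it sets the denominator. Which applies is for the trial team to decide.

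The cost is a short count for about 20 patients at a visit already planned, a CRF field and a schedule row. Some packs will not come back, and the count, though better than recall alone, can still overstate intake.

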9 PHARMACOVIGILANCE

9.1 Definitions

9.1.1 Adverse Event (AE)

An AE or adverse experience is:

Any untoward medical occurrence in a patient or clinical investigation in participants administered a medicinal product, which does not necessarily have to have a causal relationship with this treatment (the study medication).

An AE can therefore be any unfavourable and unintended sign (including an abnormal laboratory finding), symptom or disease temporally associated with the use of the study medication, whether or not considered related to the study medication.

9.1.2 Adverse Reaction (AR)

All untoward and unintended responses to a medicinal product related to any dose.

The phrase "responses to medicinal products" means that a causal relationship between a study medication and an AE is at least a reasonable possibility, i.e., the relationship cannot be ruled out. All cases judged by either the reporting medically qualified professional or the sponsor as having a reasonable suspected causal relationship to the study medication qualify as adverse reactions.

9.1.3 Severe Adverse Events

To ensure no confusion or misunderstanding of the difference between the terms "serious" and "severe", which are not synonymous, the following note of clarification is provided:

The term "severe" is often used to describe the intensity (severity) of a specific event (as in mild, moderate, or severe myocardial infarction); the event itself, however, may be of relatively minor medical significance (such as severe headache). This is not the same as "serious," which

is based on patient/event outcome or action criteria usually associated with events that pose a threat to a participant's life or functioning. Seriousness (not severity) serves as a guide for defining regulatory reporting obligations.

9.1.4 Serious Adverse Event or Serious Adverse Reaction

A serious adverse event or reaction is any untoward medical occurrence that at any dose:

- Results in death,
- Is life-threatening,

NOTE: The term "life-threatening" in the definition of "serious" refers to an event in which the participant was at risk of death at the time of the event; it does not refer to an event which hypothetically might have caused death if it were more severe.

- Requires inpatient hospitalisation or prolongation of existing hospitalisation,
- Results in persistent or significant disability/incapacity, or
- Is a congenital anomaly/birth defect.
- Other important medical events*

*Other events that may not result in death, are not life threatening, or do not require hospitalisation, may be considered a serious adverse event when, based upon appropriate medical judgement, the event may jeopardise the patient and may require medical or surgical intervention to prevent one of the outcomes listed above.

9.1.5 Expected Serious Adverse Events/Reactions

Serious adverse events that could be expected during the course of the study according to the SmPC include vomiting, haematemesis, gastrointestinal perforation, abdominal pain and dysphagia which could be related to the progression of the disease. Adverse events may also be anticipated in relation to any postoperative chemotherapy used. These would include anaemia, neutropenia (and consequences of sepsis), thrombocytopenia (and consequences of

coagulopathy), rashes, photosensitivity, taste/hearing disturbance, hair loss, discoloured urine, diarrhoea, oral ulceration and renal failure. These adverse events will be recorded in the CRF as significant clinical events.

Events which are not deemed secondary to the underlying cancer will be reported to the sponsor as a Serious Adverse Event within 24 hours of the Investigator becoming aware of the event.

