9.1.6 Suspected Unexpected Serious Adverse Reactions

A serious adverse reaction, the nature or severity of which is not consistent with the applicable product information as stated in the reference safety information in the SmPC that follows:

Common symptoms: “Abdominal pain (including upper abdomen), Flatulence, Constipation, Abdominal discomfort/ distension, Diarrhoea, Discoloured faeces, Nausea”

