9.3 Responsibilities

Principal Investigator (PI):

Checking for AEs and ARs when participants attend for treatment / follow-up.

1. Using medical judgement in assigning seriousness, causality and whether the event/reaction was anticipated using the Reference Safety Information approved for the trial.
2. Ensuring that all SAEs are recorded and reported to the sponsor within 24 hours of becoming aware of the event and provide further follow-up information

as soon as available. Ensuring that SAEs are chased with the sponsor if a record of receipt is not received within 2 working days of initial reporting.

3. Ensuring that AEs and ARs are recorded and reported to the sponsor in line with the requirements of the protocol.

Chief Investigator (CI) / delegate or independent clinical reviewer:

1. Clinical oversight of the safety of patients participating in the trial, including an ongoing review of the risk / benefit.
2. Using medical judgement in assigning the SAEs seriousness, causality and whether the event was anticipated (in line with the Reference Safety Information) where it has not been possible to obtain local medical assessment.
3. Immediate review of all SUSARs.
4. Review of specific SAEs and SARs in accordance with the trial risk assessment and protocol as detailed in the Trial Monitoring Plan.
5. Assigning Medical Dictionary for Regulatory Activities (MedDRA) or Body System coding to all SAEs and SARs.
6. Preparing the clinical sections and final sign off of the Development Safety Update Report (DSUR).

Sponsor: (NB where relevant these can be delegated to CI)

1. Central data collection and verification of AEs, ARs, SAEs, SARs and SUSARs according to the trial protocol onto a database.

2. Reporting safety information to the CI, delegate or independent clinical reviewer for the ongoing assessment of the risk / benefit according to the Trial Monitoring Plan.
3. Reporting safety information to the independent oversight committees identified for the trial (Data Monitoring Committee (DMC) and / or Trial Steering Committee (TSC)) according to the Trial Monitoring Plan.
4. Expedited reporting of SUSARs to the Competent Authority (MHRA in UK) and REC within required timelines.
5. Notifying Investigators of SUSARs that occur within the trial.
6. Checking for (annually) and notifying PIs of updates to the Reference Safety Information for the trial.

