10.4 Interim analysis and criteria for the premature termination of the trial

The trial will be terminated if there is an unacceptable number of SUSARs or SARs. Any interim data analysis will be performed at the request of the DMC.

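### Four of the five serious events that section 9.1.5 calls expected under the SmPC are missing from the section 9.1.6 list that defines a SUSAR, so a suspected reaction can be classified both ways

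*Combined protocol and SAP*

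**What the plan says.** Section 9.1.5, whose heading covers both events and reactions, states that expected serious adverse events "according to the SmPC include vomiting, haematemesis, gastrointestinal perforation, abdominal pain and dysphagia", and adds of these "which could be related to the progression of the disease". It then lists events anticipated from postoperative chemotherapy, which it does not attribute to the SmPC. On handling, it says "These adverse events will be recorded in the CRF as significant clinical events", and then: "Events which are not deemed secondary to the underlying cancer will be reported to the sponsor as a Serious Adverse Event within 24 hours".

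Section 9.1.6 defines a SUSAR as a serious adverse reaction whose nature or severity is "not consistent with the applicable product information as stated in the reference safety information in the SmPC that follows". The list given, introduced as common symptoms, is "Abdominal pain (including upper abdomen), Flatulence, Constipation, Abdominal discomfort/ distension, Diarrhoea, Discoloured faeces, Nausea".

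Section 9.2 makes any SAE that is judged both related to the IMP and unexpected a SUSAR, with expedited reporting to the MHRA. Section 9.3 asks the principal investigator to judge "whether the event/reaction was anticipated using the Reference Safety Information approved for the trial". Section 10.4 says: "The trial will be terminated if there is an unacceptable number of SUSARs or SARs".

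**The concern.** Once an event is serious and suspected to be related to the drug, expectedness alone decides whether it goes to the regulator on the expedited timetable. The protocol offers two lists for that decision, both attributed to the same product information, and they disagree on most of the serious terms that 9.1.5 names.

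The setting makes this more than a formality. Participants have bowel resected (section 4) and those allocated to ferric maltol start it after anaemia is confirmed on day 2, 3 or 5 (section 8.5). Serious gastrointestinal events in that period are ones whose cause may well be debated. An assessor who decides that the drug could have contributed, and then turns to the section headed as the list of expected reactions, could label the event expected and not start an expedited report.

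**Working it through.** No sample size, power or event-rate figure is involved, so the check sets the two lists side by side and follows one event through the classification rules.

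**Inputs.** The five terms attributed to the SmPC in 9.1.5; the seven entries in the 9.1.6 reference safety list; the classification rule in 9.2; the expectedness instruction in 9.3. The chemotherapy events in 9.1.5 are left out because that section does not attribute them to the SmPC.

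**Term-by-term comparison.**

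| Term in 9.1.5 | In the 9.1.6 list? | If serious and suspected related: 9.1.5 | If serious and suspected related: 9.1.6 with 9.2 |
|---|---|---|---|
| Vomiting | No (nausea is listed) | Expected | SUSAR |
| Haematemesis | No | Expected | SUSAR |
| Gastrointestinal perforation | No | Expected | SUSAR |
| Abdominal pain | Yes | Expected | Listed; severity must also be consistent |
| Dysphagia | No | Expected | SUSAR |

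Terms on both lists: 1 of 5. Terms that classify differently: 5 − 1 = 4, and 4/5 = 80% of the named terms. This is a share of listed words, not of events that will occur.

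**One event followed through.** Take a gastrointestinal perforation that the investigator suspects is related to ferric maltol.

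1. *Does it reach the sponsor?* Yes. It is not deemed secondary to the cancer, so 9.1.5 itself requires a report within 24 hours. Section 9.3 asks for the same for all SAEs.
2. *Is it a SUSAR?* By 9.1.6 and 9.2, yes, because the term is not in the reference list. By 9.1.5, no, because it is an expected serious event.
3. *Does any text settle the conflict?* Section 9.3 names the Reference Safety Information, and 9.1.6 is the only list carrying that label. But 9.3 does not cite 9.1.6, and nothing says that the 9.1.5 list is not for this purpose.
4. *Does it count under 10.4?* Yes under either label. If called unexpected it is a SUSAR; if called expected it is still a SAR, and the rule names both.

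The conflict therefore changes the outcome at step 2 only.

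**The case against.** The strongest defence is that 9.1.5 is not an expectedness list for drug reactions at all. It links its terms to disease progression, moves on to chemotherapy effects, and ends by separating events secondary to the cancer from those needing a prompt sponsor report. It never mentions SUSARs. Section 9.1.6 holds the only SUSAR definition, and 9.3 sends both the principal investigator and the chief investigator to the Reference Safety Information. An assessor who reads 9.1.6 and 9.3 would reach one answer.

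Much of this stands. For an event judged secondary to the cancer, no SUSAR question arises, so the conflict is confined to events suspected to be drug-related. It does not remove the conflict. The disease-progression clause says only that the events could have that cause, the heading includes reactions, and the stated source is the drug's own product information.

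The safeguards also stand. The sponsor receives the event within 24 hours, 9.2 allows classification after central review, and 9.3 provides for review by the chief investigator, DMC and TSC. They limit the harm to an expectedness label that is wrong and not corrected in time. They are not complete: the immediate chief investigator review in 9.3 is of SUSARs, so an event labelled expected would not trigger it.

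Two stronger readings are tempting. A reader might infer that a misclassified event escapes the termination rule; it does not, because 10.4 counts SARs as well as SUSARs. A reader might also express one such event as a share of the 20 patients per arm (1/20 = 5%); that arithmetic fits any single event, and the documents give no rate for these reactions, so it says nothing about how often the problem would arise.

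**Conclusion.** The inconsistency is real and visible on the face of the protocol. Four of the five serious events attributed to the SmPC in 9.1.5 would be unexpected under 9.1.6, and so SUSARs under 9.2 when suspected to be related to ferric maltol. The consequence is a missed or delayed expedited report. It is not loss of the event from the sponsor's safety data or from the 10.4 rule, and no estimate or test in the analysis changes.

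The documents cannot show which list is at fault, because the SmPC itself is not included. The 9.1.6 list is introduced as common symptoms and may be an extract. If it is complete, 9.1.5 misattributes four terms and the risk is under-reporting. If it is an extract and the full reference information covers some of the four, the 9.1.6 definition is incomplete and would produce SUSAR reports that are not needed. Either way the sections must be reconciled. A reader might infer that the SmPC attribution in 9.1.5 is simply wrong and should be deleted; that goes further than the documents allow.

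**What to change.** Check both lists against the reference safety information approved for the trial. Then reconcile 9.1.5 with 9.1.6 and 9.3 so that a single named list decides whether a suspected reaction is expected, with 9.3 citing that list by section. State in 9.1.5 that events anticipated from the disease or from chemotherapy are not used for that judgement. Whether the attribution in 9.1.5 or the content of 9.1.6 has to change should follow from the check.

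The cost is a wording amendment and possibly a few more expedited reports. Sample size, visits and analysis are untouched.
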